9.3.2 Medical History and Abbreviated Physical Examination

A medical history will be taken at Screening, and confirmed and revised if needed, at Baseline. Medical conditions that resolved 2 or more years before baseline need not be collected unless considered relevant by the Investigator.

An abbreviated physical examination including measurements of height, weight and vital signs (blood pressure, heart rate, respiration rate, and oral temperature) will be performed at Baseline and Week 12. Height will be collected at Baseline only.

9.3.3 Safety Laboratory Tests

Routine safety laboratory tests as per Appendix 16.4 will be performed at Screening, Week 6, and Week 12. Any out-of-range laboratory result that is considered clinically significant by the Investigator will be recorded as an AE and should be accessed for reproducibility by repeat testing at the discretion of the Investigator. Clinically significant laboratory abnormalities at any visit will be followed to resolution (return to normal or to the Baseline state) or until clinically stable as determined by the Investigator.

9.3.4 Pregnancy Tests

All female subjects will have a serum pregnancy test at Screening. Females of childbearing potential will take a home pregnancy urine test at Weeks 2, 8, and 10 and will have a serum pregnancy test at Weeks 6 and 12.

9.3.5 Adverse Events

9.3.5.1 Definition of Adverse Event

An AE is any untoward medical occurrence in a subject or clinical investigation subject administered a medicinal product and which does not necessarily have a causal relationship with the study drug. AEs include any unfavorable and unintended illness, sign (e.g., including an abnormal laboratory finding), symptom, clinically significant laboratory test abnormality, or disease temporally associated with the use of a medicinal product that has appeared or

worsened during the course of the clinical trial, regardless of causal relationship to the study drug(s) under study.

9.3.5.2 Documenting Adverse Events

It is the responsibility of the Investigator to document all AEs that occur during the course of the study. The AEs should be documented as a single medical diagnosis. When this is not possible, the AE should be documented in terms of signs and/or symptoms observed by the Investigator or reported by the subject at each study visit.

All AEs occurring after the subject signs the informed consent through the last study visit must be reported, regardless of whether or not the AEs are considered drug-related. All AEs, whether in response to a query, observed by the study site personnel, or reported spontaneously by the subject, will be recorded.

At each visit during the study, the subject will be assessed for the occurrence of new and ongoing AEs. Dermal safety and tolerability that result in the subject's requiring a concomitant therapy or discontinuation from the study will be reported as an AE. The following data will be collected on all AEs and recorded on the appropriate CRF:

- Event name (diagnosis preferred, if unknown, record the signs/symptoms)
- Onset date and end date
- Maximum intensity (severity)
- Seriousness
- Action taken regarding study drug
- Corrective treatment, if given
- Outcome

In addition, the Investigator's assessment of causality will be recorded.

Vital sign abnormalities are to be recorded as AEs only if they are clinically significant (for example: are symptomatic, requiring corrective treatment, leading to discontinuation or fulfilling a seriousness criterion).

Subjects will be questioned about any concurrent illness or systemic sign or symptom including but not limited to fatigue, loss or change in taste, nausea, vomiting, alopecia, diarrhea, and muscle spasms. Any incidence of these systemic signs or symptoms will be reported on the AE eCRF.

9.3.5.3 Serious Adverse Events

All AEs will be assessed as either serious or non-serious.

An SAE or serious adverse reaction is defined as any untoward medical occurrence that at any dose:

- Results in death
- Is immediately life threatening, (the term "life threatening" in the definition of "serious" refers to an event in which the subject is at risk of death at the time of the event; it does not refer to an event which hypothetically might have caused death if it were more severe)
- Requires in subject hospitalization or prolongation of existing hospitalization (hospitalization for elective surgery for a baseline condition is not considered an AE)
- Results in persistent or significant disability/incapacity (permanent or substantial disruption of a person's ability to conduct normal life functions)
- Is a congenital anomaly/birth defect
- Is a medically important event that may not be immediately life threatening or result in death or hospitalization, but may jeopardize the subject and may require medical or surgical intervention to prevent any of the above listed outcomes

Note: A spontaneous abortion will be considered an SAE, and must be reported per Reporting of SAEs under Section 9.3.5.6.

9.3.5.4 Assessment of Severity

The severity assigned to an AE should be determined by the maximum severity of the AE. The categories described below should be used to estimate the severity of AEs:

- Mild: Transient or mild discomfort; no limitation in activity; no medical intervention/therapy required
- Moderate: Mild to moderate limitation in activity; some assistance may be needed; no or minimal medical intervention/therapy required
- Severe: Marked limitation in activity; some assistance usually required; medical intervention/therapy required; hospitalization or prolongation of current hospitalization possible; may be incapacitating or life threatening

9.3.5.5 Assessment of Causality

The Investigator should assess the relationship of the AE, if any, to the study drug. The following should be taken into account when assessing SAE causality:

- Positive temporal relationship to study drug, such as if the study drug was withdrawn and the SAE resolved or the event recurred after re-introduction.
- If there is a reasonable possibility that the AE is associated with an underlying or concomitant illness.
- Possible association with previous or concomitant therapy.
- No temporal relationship to the study drug and/or a more likely alternative etiology exists.
- If the AE is directly related to study procedures or a lack of efficacy.

The following classifications should be used when evaluating the relationship of AEs and SAEs to the investigational drug.

- 1. **None**: No relationship between the experience and the administration of study drug; related to other etiologies such as concomitant medications or subject's clinical state.
- 2. **Unlikely**: The current state of knowledge indicates that a relationship is unlikely.
- 3. **Possibly**: A reaction that follows a plausible temporal sequence from administration of the study drug and follows a known response pattern to the suspected study drug. The reaction might have been produced by the subject's clinical state or other modes of therapy administered to the subject.
- 4. **Probably:** A reaction that follows a plausible temporal sequence from administration of the study drug and follows a known response pattern to the suspected study drug. The reaction cannot be reasonably explained by the known characteristics of the subject's clinical state or other modes of therapy administered to the subject.
- 5. **Definitely**: A reaction that follows a plausible temporal sequence from administration of the study drug and follows a known response pattern to the suspected study drug and can be confirmed with a positive re-challenge test or supporting laboratory data

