9.3.5.8 Expedited Serious Adverse Event Reports

An AE, whether serious or non-serious, is designated unexpected (unlabeled) if it is not reported in the clinical safety section of the Investigator Brochure or if the event is of greater frequency, specificity or severity.

Expedited SAE reports are those that document AEs that are both unexpected based on the reference document (Investigator Brochure) and are related (i.e., the relationship cannot be ruled out) to the study drug. These expedited reports are subject to reporting timelines of 7 (SAEs) and/or 15 (non SAE) calendar days to the regulatory reporting agency(ies). PellePharm will notify regulatory authorities of these AEs and all participating investigational centers in writing for submission by the Investigator to the IRB/IEC. This notification will be in the form of a Safety Update to the Investigator Brochure (i.e., "15-day letter").

Upon receiving such notices, the Investigator must review and retain the notice with the Investigator Brochure and immediately submit a copy of this information to the responsible IRB/IEC according to local regulations. The Investigator and IRB/IEC will determine if the informed consent requires revision. The Investigator should also comply with the IRB/IEC procedures for reporting any other safety information.

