6.8.2 Adverse Events

All AEs that occur during the study will be recorded and classified on the basis of Medical Dictionary for Regulatory Activities (MedDRA) terminology. Treatment-emergent Aes (TEAEs) are defined as Aes with an onset on or after the date of the first study drug application. Adverse events noted prior to the first study drug administration that worsen after Baseline will also be reported as Aes and included in the summaries.

Treatment-emergent Aes will be summarized by treatment group, the number of subjects reporting a TEAE, SOC, preferred term, severity, relationship to study drug (causality), and seriousness. When summarizing Aes by severity and relationship, each subject will be counted once within a system organ class or a preferred term by using the event with the highest severity and greatest relationship within each classification.

If relationship to study drug is reported as unknown, possible, probable or definite, then this is defined as related. If relationship to study drug is reported as unlikely or not related, then this is defined as unrelated.

Serious Aes will be summarized by treatment group, severity and relationship to study drug.

Listings will be presented for all adverse events as well as for serious adverse events and adverse events leading to study drug withdrawal.

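### All three related causality classes require a known response pattern, so a well-timed reaction that is new for the drug is tabulated by elimination as unrelated

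*Protocol*

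**What the plan says.** Protocol 9.3.5.5 gives five classes. Possibly and Probably open with the same sentence, which asks for plausible timing "from administration of the study drug and follows a known response pattern to the suspected study drug". They differ only in whether the subject's clinical state or other therapy could explain the event. Definitely also requires plausible timing, and the reaction must be one that "follows a known response pattern to the suspected study drug and can be confirmed with a positive re-challenge test or supporting laboratory data". The other two classes carry no pattern condition. None is "No relationship between the experience and the administration of study drug; related to other etiologies", and Unlikely reads "The current state of knowledge indicates that a relationship is unlikely".

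SAP 6.8.2 reduces the grades to two groups. On one side: "If relationship to study drug is reported as unknown, possible, probable or definite, then this is defined as related". On the other: "If relationship to study drug is reported as unlikely or not related, then this is defined as unrelated".

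Protocol 9.3.5.8 sets the causality condition for expedited reporting separately: "Expedited SAE reports are those that document AEs that are both unexpected based on the reference document (Investigator Brochure) and are related". It explains related, in parentheses, as a relationship that has not been ruled out, and it does not refer to the five classes.

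**The concern.** Safety and tolerability is the first primary objective (Protocol 5, SAP 3). Inclusion criterion 3 states that systemic exposure in humans after topical use is not known. Protocol 4 describes topical experience in mini-pig skin, mice and human tumour explants, and Protocol 8 calls the gel non-irritating. Class effects seen with oral treatment, such as taste loss and cramps, do have a known pattern. A local reaction specific to the gel, or an unlisted systemic effect, may have none. Those are the reactions a trial at this stage most needs to be able to attribute.

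If the scale gives such reactions no related grade, the error runs one way: fewer events counted as related. It could enter the unblinded looks at limited safety results planned after Cohorts 1 and 2 and again after Cohort 3 (SAP 6.1.6), as well as the final tables. It also reaches the efficacy analysis. SAP 6.4.3 keeps in the Per Protocol population subjects who discontinue because of a treatment-related adverse event. A subject whose event was graded Unlikely loses that route.

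**Working it through.** The plan states no figure on this point, so the check is mainly a tracing of definitions. The test case is a reaction with plausible timing, no alternative cause and no established response pattern.

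| Class (Protocol 9.3.5.5) | What it requires | Met by the test case? | SAP 6.8.2 group |
|---|---|---|---|
| None | no relationship; another cause | No, there is no other cause | unrelated |
| Unlikely | current knowledge points against a relationship | Not strictly; absence of knowledge is not evidence against | unrelated |
| Possibly | timing and known pattern | No, pattern missing | related |
| Probably | timing and known pattern, no other explanation | No, pattern missing | related |
| Definitely | timing and known pattern, with re-challenge or laboratory support | No, pattern missing | related |

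**Step 1.** The conditions in the three related classes are joined by *and*, so 3 of 3 related classes fail on the pattern condition alone.

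**Step 2.** The investigator must still record a grade. Only Unlikely and None remain. Neither fits well, so the placement is by elimination. Both map to unrelated.

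**Step 3.** The SAP's route from unknown to related would rescue the case only if unknown could be recorded, and it is not one of the five classes. The table footnotes also differ: Table 14.3.2.1.1 says unknown counts as related, while Table 14.3.2.1.4 does not mention it.

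**Step 4.** The section sits badly with itself. Its list of considerations names resolution on withdrawal and recurrence on re-introduction as a positive temporal relationship, and does not name a known pattern. Yet a new reaction that recurs on re-introduction still fails even Possibly as worded.

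**Size.** Each cohort has 6 subjects on active gel (Protocol 5.1, SAP 4.1). Related TEAEs are counted once per subject. If all 6 are in the Safety population and the subject concerned has no other related TEAE, one misgraded subject changes the regimen's rate by 1/6 = 0.167, or 16.7 percentage points. If the subject has another related TEAE, the subject-level rate changes by 0. The documents give no basis for predicting how many such reactions will occur, so only the step per subject can be stated.

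**Comparison with the expediting rule.** Section 9.3.5.5 asks whether the reaction shows a known pattern. Section 9.3.5.8 asks whether a relationship has been ruled out. An event graded Unlikely fails the first test but can pass the second. Neither section says which governs.

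**The case against.** The strongest reply is that the safety reporting does not depend on this scale as much as it may seem, and a good part of that stands.

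- A reader might infer that novel reactions drop out of expedited reporting. The documents do not support this. Section 9.3.5.8 applies its own test, and Unlikely is not the same as ruled out. Section 9.3.5.6 sends every SAE to the sponsor within 24 hours whatever its causality. It also has the investigator notify the IRB/IEC of unexpected SAEs that involve risk to subjects, with no causality class named. What remains is a conflict between two meanings of related, and a risk of under-reporting if the recorded class is used in practice as the gate.
- A reader might also infer that the category of unexpected and related events is almost empty. That does not follow. Section 9.3.5.8 also treats an event as unexpected when its frequency, specificity or severity is greater. Such an event can follow a known pattern and be graded Possibly or higher. Nor can it be assumed that every event missing from the Brochure's clinical safety section lacks a known pattern.
- Novel reactions stay visible. TEAEs are tabulated by arm, vehicle included, without a causality filter (Table 14.3.2.1.2). The listed local signs and the systemic symptoms are summarised regardless of causality (Tables 14.3.1.2.1 and 14.3.1.2.2).
- An investigator may apply the considerations list sensibly and grade such an event Possibly anyway. That is plausible, but it means departing from the written definition, and different investigators may do so differently.

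None of this repairs the related/unrelated split. The 24-hour rule covers SAEs only, so non-serious novel reactions depend on this scale for how they are classed in the tables.

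**Conclusion.** The point holds for the relatedness tabulation. As worded, the scale has no related class for a well-timed reaction without an established pattern, and the SAP then counts it as unrelated. Tables 14.3.2.1.1 and 14.3.2.1.4 can understate novel reactions by at most 16.7 percentage points per misgraded subject in a regimen, under the two conditions given above. That figure is a ceiling, not an expected effect. Per Protocol membership can also be affected, if relatedness in SAP 6.4.3 is taken from the same grade.

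The conclusion assumes that investigators apply the definitions literally and that the form offers only the five protocol classes. It does not extend to a claim that expedited reporting is blocked. On that, the finding is only that 9.3.5.5 and 9.3.5.8 use different tests and should be reconciled. The change is worth making because the error has one direction, touches a primary objective and is cheap to remove.

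**What to change.** 1. In Protocol 9.3.5.5, remove the known-pattern condition from Possibly, so that plausible timing is enough even where another explanation might exist. This alone gives the test case a related class. Making the pattern a supporting feature in Probably and Definitely is optional.
2. In Protocol 9.3.5.8, state that its own test, a relationship not ruled out, decides expediting whatever class the investigator has recorded.
3. Align the SAP's unknown category with the protocol scale: either add an unknown grade to 9.3.5.5, or limit the SAP 6.8.2 rule to events with a missing assessment and say so. Use the same footnote in Tables 14.3.2.1.1 and 14.3.2.1.4.
4. In SAP 6.4.3, say that a related adverse event means related as defined in 6.8.2.

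The cost is a wording amendment to the protocol and SAP, with matching instructions to the site. Design, sample size and treatment are unchanged. The downside is that a few more events will be counted as related.

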9.3.5.6 Reporting of Serious Adverse Events

When new significant information is obtained as well as when the outcome of an event is known, the Investigator should record the information on a new SAE form. If the subject was hospitalized, a copy of the discharge summary must be included as part of the subject's medical file. In all instances, the Investigator should follow up with subjects until the outcome of the SAE is known.

All AEs spontaneously reported by the subject and/or in response to an open question from study personnel or revealed by observation, physical examination or other diagnostic procedures will be recorded on the AE eCRF. Any clinically relevant change in laboratory assessments or other clinical findings is considered an AE and must be recorded on the AE eCRF. All AEs are to be followed until the event resolves or the clinical course is stabilized.

For SAEs, a SAE form must be completed with as much information as possible and submitted in the time frame described below.

PellePharm must be notified of all SAEs (regardless of casual relationship to study drug) within 24 hours of first knowledge of the event by the Investigator or other study personnel by faxing a completed SAE form to the contact information below.

Safety Reporting Contact		
Name:	PPD	
Telephone:	PPD	
	PPD	
Mobile:	PPD	
Facsimile:	PPD	
Email:	PPD	

If there are serious, unexpected AEs associated with the use of the study drug, PellePharm will notify the appropriate regulatory agency(ies) and all appropriate parties on an expedited basis. It is the responsibility of the Investigator to promptly notify the IRB/IEC of all unexpected SAEs involving risk to human subjects.

The Investigator should take all appropriate measures to ensure the safety of the subjects, notably and should follow a subject with an SAE until the event has resolved or the condition has stabilized. This may imply that follow-up will continue after the subject has left the study, and that additional investigations may be requested by PellePharm.

9.3.5.8 Expedited Serious Adverse Event Reports

An AE, whether serious or non-serious, is designated unexpected (unlabeled) if it is not reported in the clinical safety section of the Investigator Brochure or if the event is of greater frequency, specificity or severity.

Expedited SAE reports are those that document AEs that are both unexpected based on the reference document (Investigator Brochure) and are related (i.e., the relationship cannot be ruled out) to the study drug. These expedited reports are subject to reporting timelines of 7 (SAEs) and/or 15 (non SAE) calendar days to the regulatory reporting agency(ies). PellePharm will notify regulatory authorities of these AEs and all participating investigational centers in writing for submission by the Investigator to the IRB/IEC. This notification will be in the form of a Safety Update to the Investigator Brochure (i.e., "15-day letter").

Upon receiving such notices, the Investigator must review and retain the notice with the Investigator Brochure and immediately submit a copy of this information to the responsible IRB/IEC according to local regulations. The Investigator and IRB/IEC will determine if the informed consent requires revision. The Investigator should also comply with the IRB/IEC procedures for reporting any other safety information.

9.3.5.9 Other Required Safety Assessments

A clinically significant worsening from Baseline of any abnormal study assessment, such as laboratory test, physical examination, or vital signs, should be considered an AE and recorded accordingly. If possible, a diagnosis for the clinically significant study assessment should be provided by the Investigator (e.g., urinary tract infection or anemia). In the absence of a diagnosis, the abnormal study assessment itself should be listed as the AE (e.g., bacteria in urine or decreased hemoglobin).

An abnormal study assessment is considered clinically significant if the subject has one or more of the following related to the abnormal study assessment:

- 1. Concomitant clinical signs or symptoms
- 2. Further diagnostic testing or medical/surgical intervention
- 3. A change in the dose of study drug or is discontinued from the study

PellePharm, Inc.
Dose Escalating in Sporadic Basal Cell Carcinomas

Repeat testing to determine whether the result is abnormal, in the absence of any of the above criteria, does not necessarily meet clinically significant criteria.

10. STATISTICS

All statistical processing will be performed using SAS[®] unless otherwise stated. If determined appropriate by the Sponsor, limited safety and efficacy interim analysis on tumor shrinkage and biomarkers may be performed.

No inferential testing will be performed. Descriptive statistics will be used to provide an overview of the efficacy and safety results. For categorical parameters, the number and percentage of subjects in each category will be presented. For continuous parameters, descriptive statistics will include n (number of subjects), mean, and standard deviation, median, minimum, and maximum.

No imputation will be made for the primary endpoint. For the secondary endpoint, the last observation carried forward method (LOCF) will be used to impute missing efficacy data (i.e., the last available on-therapy observation for a subject will be used to estimate subsequent missing data points). No imputations will be made for missing safety data.

A statistical analysis plan (SAP), describing all statistical analyses will be provided as a separate document. The SAP will be finalized prior to unblinding of the study treatments.

